5.3. Initiation of Treatment for Proliferative Diabetic Retinopathy

Treatment for PDR must not be given until one of the following criteria has been met:

1. The eye has PDR with high-risk characteristics, defined as:
 - a. Neovascularization of the disc (NVD) greater than Standard photograph 10A (1/4 to 1/3 disc area), or
 - b. Any NVD with pre-retinal or vitreous hemorrhage, or
 - c. Neovascularization elsewhere (NVE) greater than 1/2 disc area with pre-retinal or vitreous hemorrhage.
2. The eye has vitreous hemorrhage requiring treatment that is presumed to be from PDR (either NV identified on FA or unable to assess NV due to the density of the hemorrhage, but there is no other attributable cause).

3. NV of the iris (at least 2 cumulative clock hours), definitive NV of the angle, or neovascular glaucoma development on clinical exam (photographic documentation not required)
4. The central reading center has confirmed NV is present within the 7-modified fields and approval from Sponsor medical monitor has been received to initiate treatment prior to high-risk characteristics being present.

Note: Treatment for NVE outside of the 7-modified fields without the presence of pre-retinal or vitreous hemorrhage is discouraged.

5.4. Initiation of Treatment for Center-involved Diabetic Macular Edema

Treatment for CI-DME must not be given until all the following criteria have been met:

1. At least a 10% increase in OCT central subfield thickness from baseline as confirmed by the central reading center.
2. Confirmed visual acuity loss presumed to be from DME, which is defined as either
 - a. at least a 10-letter loss from baseline at a single visit, OR
 - b. 5- to 9-letter losses at 2 consecutive visits that are at least 21 days apart.

5.5. Strategies for Recruitment and Retention

The Sponsor does not anticipate any specific challenges in meeting recruitment goals of enrolling and retaining a total of approximately 80 participants in this study. Participants will be recruited continuously until the planned sample size is achieved. Participants who withdraw or are withdrawn during Screening, as well as participants who discontinue, may be replaced (see [Section 5.6.2](#)).

The anticipated length of participation in the study of approximately 32 weeks is not expected to be challenging to participants. Financial support for meals and miscellaneous expenses will be available during the study, as appropriate and based on local regulations and guidelines. Use of visit transport services may also be incorporated into the trial to support the participant in maintaining study visit compliance. A description of the study will be included in local clinical trial databases, as required.

5.6. Participant Withdrawal

5.6.1. Reasons for Withdrawal

A participant may be withdrawn from study treatment for the following medical or administrative reasons:

- Occurrence of an AE that represents an unacceptable risk to the participant and when continued participation in the investigational study is not warranted, in the judgment of the

investigator, Sponsor, or medical monitor. The investigator must follow the participant until the AE resolves or is stable unless the participant is lost to follow up.

- Discontinuation of the investigational product for liver enzyme abnormalities (confirmed upon repeat testing) is required if:
 - ALT or AST $\geq 8 \times$ ULN;
 - ALT or AST $\geq 5 \times$ ULN for more than 2 weeks;
 - ALT or AST $\geq 3 \times$ ULN and (total bilirubin $> 2 \times$ ULN or international normalized ratio (INR) > 1.5);
 - ALT or AST $\geq 3 \times$ ULN with new symptoms of fatigue, nausea, vomiting, right upper quadrant pain or tenderness, dark urine, or new clinical signs of fever, rash, jaundice, eosinophilia ($> 5\%$), or encephalopathy.
- Treatment with a prohibited concomitant medication other than the use of appropriate medications for the treatment of AEs under direction of the investigator.
- Participant noncompliance, defined as refusal or inability to adhere to the trial schedule or procedures.
- At the request of the participant (e.g., participant withdraws consent), investigator, Sponsor, or regulatory authority.
- Pregnancy.

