15. SCHEDULE OF EVENTS

Table 2 **Schedule of Assessments**

Visit Number Week Day Time Window (days) ^a	Screening		Treatment							Follow-up
	1	2 (Baseline) 1 -28 to -2	3 4 28 ±3	4 8 56 ±3	5 12 84 ±3	6 16 112 ±3	7 20 140 ±3	8 (EOT/ET) ^b 24 168 ±3	9 (EOS) 28 196 ±3	
Informed consent and optional consent for aqueous humor sample collection ^c	X									
Informed consent for DNA banking ^d	X									
Demographics	X									
Medical history	X									
Inclusion/exclusion criteria ^e	X	X								
Physical examination	X	X							X	
Vital signs (seated)	X	X	X	X	X	X	X	X		
Pregnancy test (in WOCBP) ^f	X	X	X	X	X	X	X	X		
Laboratory tests ^g	X	X	X	X	X	X	X	X		X
12-lead electrocardiogram	X								X	X
HbA1c			X		X				X	
Extended ophthalmoscopy	X	X	X	X	X	X	X	X		X
Slit lamp examination	X	X	X	X	X	X	X	X		X
Intraocular pressure	X	X	X	X	X	X	X	X		X
Gonioscopy	X	X		X		X		X		X
SD-OCT	X	X	X	X	X	X	X	X		X
OCT-A (if available at the site) ^h			X						X	
Visual acuity ⁱ	X	X	X	X	X	X	X	X		X
Fundus photography	X	X	X	X	X	X	X	X		X
Fluorescein angiography ^j	X				X			X		
VF with perimetry and/or microperimetry (if available at the site) ^h			X						X	
Workplace Productivity and Activity Impairment General Health questionnaire			X		X		X		X	
Administration of study agent ^k			X	X	X	X	X	X		
Dispense study agent			X	X	X	X	X	X		
Study agent accountability			X	X	X	X	X	X	X	

Visit Number Week Day Time Window (days) ^a	Screening		Treatment							Follow-up
	1	2 (Baseline)	3	4	5	6	7	8 (EOT/ET) ^b	9 (EOS)	
	-28 to -2	1	4	8	12	16	20	24	28	
		1	28	56	84	112	140	168	196	
Optional aqueous humor collection ¹		X						X		
PK blood sample collection (for plasma extraction) ^m		X	X	X	X	X	X	X	X	
Biomarker plasma aliquots ^m		X						X	X	
Pharmacogenomics blood sample (and optional DNA banking sample)		X ^d								
Flow cytometry/CBC blood sample collection ^m		X						X		
Prior and concomitant medication review ⁿ	X	X	X	X	X	X	X	X	X	
Adverse events	X	X	X	X	X	X	X	X	X	
Study completion										X

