17.1.2. Procedures

17.1.2.1. Guidelines for Evaluation and Follow-up Testing of Mild Liver Enzyme Elevations

Guidelines for evaluation and follow-up testing of mild liver enzyme elevations (ALT or AST $\geq 3 \times$ ULN but $< 5 \times$ ULN without bilirubin elevations) include:

- A review of symptoms, history, and physical examination to assess for signs of liver enzyme elevation etiology, and updates to the CRF should be made as appropriate (see [Section 17.1.3](#)).
- Repeat ALT, AST, bilirubin, and ALP testing, and perform initial gamma-glutamyl transferase (GGT) testing, *within 1 week* with the central laboratory to confirm the results.
 - In cases in which the central laboratory is not immediately available (e.g., if the logistics are such that the participant's repeat specimen would not reach the central laboratory in a reasonable timeframe), ALT, AST, and bilirubin (total and direct) will be evaluated by the local laboratory and results will be made available to the investigator and to Alkahest as soon as possible.
- If elevations are confirmed on repeat testing, follow-up testing of ALT, AST, bilirubin, ALP, and GGT should be repeated at a minimum of every 2 weeks until ALT and AST values have decreased to $< 2 \times$ ULN.
- Once values reach $< 2 \times$ ULN, standard per protocol laboratory assessment is adequate.

17.1.2.2. Guidelines for Evaluation and Follow-up Testing of Moderate to Severe Liver Enzyme Elevations

Guidelines for evaluation and follow-up testing of moderate (ALT or AST $\geq 5 \times$ ULN without bilirubin elevations) to severe (ALT or AST $\geq 3 \times$ ULN with an elevation of total bilirubin $> 2 \times$ ULN) liver enzyme elevations include:

- A review of symptoms, history, and physical examination findings to assess for signs of liver enzyme elevation etiology, and updates to the CRF should be made as appropriate (see [Section 17.1.3](#)).

- Repeat ALT, AST, bilirubin, and ALP testing, and perform initial GGT testing, within 48-72 hours with the central laboratory to confirm the results.
 - In cases in which the central laboratory is not immediately available (e.g., if the logistics are such that the participant's repeat specimen would not reach the central laboratory in a reasonable timeframe), ALT, AST, and bilirubin (total and direct) will be evaluated by the local laboratory and results will be made available to the investigator and to Alkahest as soon as possible.

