- If confirmed on repeat testing, close observation should be initiated, follow-up testing of ALT, AST, bilirubin, ALP, and GGT should be repeated weekly until resolved, and additional one-time tests should be obtained as described in [Sections 17.1.2.3](#) through [17.1.2.8](#), in consultation with the Medical Monitor.
- Once values reach $< 2 \times$ ULN, standard per protocol laboratory assessment is adequate.

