17.1.2.3. Clinical Chemistry

- Obtain albumin, PT or INR, creatinine kinase, creatinine kinase MB test (CK-MB), ceruloplasmin, α -1 antitrypsin, transferrin, amylase, lipase, glucose, cholesterol, and triglycerides.

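### INR above 1.5 is a required stop at confirmed ALT/AST ≥3× ULN, but the work-up for 3× to <5× ULN without bilirubin elevation orders neither PT nor INR

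*Protocol*

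**What the plan says.** **Stopping rule (Protocol 5.6.1).** Discontinuation is mandatory for several patterns of liver abnormality, each confirmed on repeat testing. One pattern is ALT or AST ≥3× ULN with either total bilirubin >2× ULN or "international normalized ratio (INR) > 1.5". The two are alternatives, so INR can trigger the stop by itself when bilirubin is normal.

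**Work-up for 3× to <5× ULN without bilirubin elevation (Protocol 17.1.2.1).**
- Within 1 week: "Repeat ALT, AST, bilirubin, and ALP testing, and perform initial gamma-glutamyl transferase (GGT) testing".
- Once confirmed, until ALT and AST fall below 2× ULN: "follow-up testing of ALT, AST, bilirubin, ALP, and GGT should be repeated at a minimum of every 2 weeks".
- If the central laboratory cannot be reached in time: "ALT, AST, and bilirubin (total and direct) will be evaluated by the local laboratory".
- Clinical review: "A review of symptoms, history, and physical examination to assess for signs of liver enzyme elevation etiology".

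**Where the appendix orders PT or INR.** Section 17.1.2.3 reads "Obtain albumin, PT or INR, creatinine kinase", followed by other chemistry. The moderate-to-severe work-up in 17.1.2.2 leads to it, saying that after confirmation "additional one-time tests should be obtained as described in" the later subsections.

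**Routine laboratory tests.** Protocol 7.1.1.2.6 and SAP 3.4.2.2 both include a coagulation panel of PTT and PT. Neither names INR, and both refer timing to the Section 15 schedule. In that schedule, the note to the row "Laboratory tests ^g" names hematology, chemistry and urinalysis, with serology at Screening only. Coagulation is not mentioned.

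**The concern.** A mandatory stopping criterion needs a measurement. The participant for whom the INR criterion decides the matter has confirmed enzymes between 3× and 5× ULN, normal bilirubin and no qualifying symptom or sign. That is the participant whom 17.1.2.1 covers, and followed as written it never produces the value that the rule needs. Unless the investigator or the laboratory manual adds the test, such a participant could be followed as mild and stay on drug.

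The rule addresses a known concern with this drug. SAP Section 1 says that the study was terminated after liver enzyme findings in other AKST4290 studies.

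**Working it through.** There is no planned figure to reproduce. The check sets each stopping criterion beside the places where its measurement is ordered, and then works out the timing.

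**Step 1. Can a raised INR move a participant out of the mild tier?** Entry to 17.1.2.2 needs ALT or AST ≥5× ULN, or ≥3× ULN with total bilirubin >2× ULN. INR is not an entry condition. The severity grading in 8.2.1 does not use INR either: 3× to <5× ULN is mild, and bilirubin is what makes it severe. A participant with a raised INR and nothing else therefore stays under 17.1.2.1.

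**Step 2. Criterion against measurement for that participant.**

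| Stopping criterion (5.6.1) | In the 17.1.2.1 work-up? | In the Section 15 laboratory note? |
|---|---|---|
| ALT/AST thresholds | Yes, all three test lists | Yes (chemistry) |
| Total bilirubin >2× ULN | Yes, all three test lists | Yes (chemistry) |
| New symptoms or clinical signs | Yes, clinical review | Not a laboratory item |
| Eosinophilia >5% | No; the differential is in 17.1.2.6, reached from 17.1.2.2 | Yes (hematology, which includes the differential per 7.1.1.2.6) |
| INR >1.5 | No; PT or INR is in 17.1.2.3, reached from 17.1.2.2 | No; PT appears only in the 7.1.1.2.6 and SAP 3.4.2.2 lists |

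The 1-week repeat is also the confirmation on which 5.6.1 depends, so the missing assay is missing at the point of decision.

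**Step 3. Timing if PT is drawn at every scheduled laboratory visit.** Inputs: Week 4 is Day 28 and Week 8 is Day 56, each ±3 days (Section 15); dosing is two tablets a day (6.1.4); work-up liver tests come at least every 14 days (17.1.2.1).

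- Nominal spacing: 56 − 28 = 28 days, or 28 × 2 = 56 tablets.
- Longest spacing within the windows: (56 + 3) − (28 − 3) = 34 days, or 34 × 2 = 68 tablets.
- Spacing if PT/INR joined the 17.1.2.1 follow-up: at most 14 days, or 14 × 2 = 28 tablets.

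The 34 days is not an upper bound. Section 13.3 and the notes to Table 2 allow window extensions and missed assessments because of COVID-19, so the gap can be longer. On this reading the eosinophil count has the same spacing, because it too comes only at scheduled visits.

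**Step 4. Timing if coagulation is not drawn at visits.** Neither document then orders a PT or INR during treatment for a participant who stays in the mild tier.

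I give no count of work-up draws without PT. It would depend on when the first elevation falls, on whether the investigator times the draws to coincide with visits (the intervals allow it), and on how long enzymes stay above 2× but below 5× ULN.

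**The case against.** The strongest reply is that PT is a study test and the Section 15 note is merely an incomplete summary. Protocol and SAP both list coagulation among the laboratory tests, and the note restricts only serology, to Screening. It would be odd to name PT and PTT in both documents and never draw them. Section 17.1.2.3 treats PT and INR as interchangeable, so the absence of the word INR from the panel matters little. Section 7.2.1 sends sites to a laboratory manual for the full list of evaluations. All of this stands. A reader might infer from the note that PT is measured at none of the six laboratory visits from Week 4 to Week 24; the documents do not support that as the preferred reading. What remains is a conflict to be resolved and, even on the favorable reading, a slower clock for INR than for the enzymes.

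A reader might also infer that INR is the only stopping criterion left out of the mild work-up. It is not, because eosinophilia is missing too. The difference is that the Section 15 note clearly schedules hematology and says nothing on coagulation.

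Third, 17.1.2.1 is a guideline listing what the evaluation includes, whereas 5.6.1 is mandatory, so an investigator applying 5.6.1 has good reason to check INR. Mild elevations confirmed on repeat are recorded as adverse events, safety laboratory values are reviewed cumulatively (8.6), and withdrawal for an adverse event remains open. These safeguards lower the risk. But 17.1.1 directs that these abnormalities be followed using the appendix procedures, and a required stop should not rest on a test that is left to initiative.

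Finally, three participants were on drug when the study was terminated. Nothing in the documents suggests that a stop was missed, and the liver findings in other studies are described as enzyme elevations, with no mention of INR.

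**Conclusion.** The gap is real and minor. For confirmed ALT/AST of 3× to <5× ULN without bilirubin elevation, the work-up does not order the test needed to apply a mandatory stopping criterion. Whether routine visits supply it cannot be settled from the protocol and SAP, because the laboratory lists and the Section 15 note disagree.

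Those affected would be participants in that enzyme range with INR >1.5 and no other trigger. The documents give no frequency for this group and I assume none. If PT is run at visits, detection could lag by about 28 days nominally, and by 34 days or more with windows and COVID-19 allowances. If it is not, detection depends on the investigator or the laboratory manual.

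Confidence is medium, mainly because the laboratory manual is not available. Dosing has ended and the SAP is limited to listings, so the point has no bearing on this study's analysis. It matters only for a restart or for reuse of this liver text.

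**What to change.** In Protocol 17.1.2.1, add PT/INR to the 1-week repeat, to the follow-up at least every 2 weeks, and to the local-laboratory fallback. In the Section 15 laboratory note, add coagulation (PT/INR) so that it agrees with 7.1.1.2.6 and SAP 3.4.2.2. No threshold changes.

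The cost is one assay, and possibly one extra tube, at draws that already take place, plus wording in two places.

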5.6.2. Handling of Participant Withdrawals

Participants will be encouraged to complete the study and all assessments. Participants may voluntarily withdraw at any time, and the investigator may discontinue individual participants from the study at any time.

Approximately 80 participants are planned for enrollment to provide data for 69 completed participants (i.e., participants who complete the 24-week assessments). Participants who withdraw or are withdrawn may be replaced; enrollment will continue to ensure that data from 69 completed participants are available. Participants who withdraw or are withdrawn due to AEs or adverse reactions based on study procedures will not be replaced.

Participants who have received at least 1 tablet of study drug but are withdrawn or withdraw from the study will be encouraged to complete the end-of-treatment (EOT) procedures. The primary reason for study discontinuation will be documented on the electronic case report form (eCRF).

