6.1.4. Dosing and Administration

Study drug will be self-administered orally b.i.d., approximately 12 hours apart. AKST4290 will be administered as a TDD of 800 mg (400 mg b.i.d.). Matching placebo will be self-administered orally b.i.d. following the same dosing instructions as AKST4290.

Participants will receive training on study drug administration prior to initial study drug administration at Visit 2. Study drug will be self-administered in the clinic under the supervision of study personnel during every in-clinic visit of the Treatment Period (Visits 2-8) after any pre-dose assessments (including PK sample collection), and then self-administered at home between study visits.

When study drug is dispensed, participants will receive a total of 5 packets, which represents a 5-week supply (4 weeks of treatment plus an additional week). Study drug accountability will be assessed by packet.

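### Symptomatic ALT/AST elevations at 3 to below 5 × ULN, which must stop once confirmed, may wait up to 1 week for the confirmatory repeat; asymptomatic elevations at 5 to below 8 × ULN, which need not yet stop, get 48–72 hours

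*Protocol*

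**What the plan says.** Protocol Section 5.6.1 introduces its liver stopping rule with "Discontinuation of the investigational product for liver enzyme abnormalities (confirmed upon repeat testing) is required if" and then gives four limbs for ALT or AST:

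- at least 8 × ULN;
- at least 5 × ULN lasting more than 2 weeks;
- at least 3 × ULN together with total bilirubin above 2 × ULN or INR above 1.5;
- at least 3 × "ULN with new symptoms of fatigue, nausea, vomiting, right upper quadrant pain or tenderness, dark urine, or new clinical signs of fever, rash", with jaundice, eosinophilia and encephalopathy completing the list of signs.

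The timing of the repeat is set in the appendix. Section 17.1.2.1 covers 3 to below 5 × ULN without bilirubin elevation. Its first step is "A review of symptoms, history, and physical examination to assess for signs of liver enzyme elevation etiology". The repeat of ALT, AST, bilirubin and ALP, with a first GGT, follows as "testing, *within 1 week* with the central laboratory to confirm the results". Section 17.1.2.2 covers at least 5 × ULN without bilirubin elevation, and at least 3 × ULN with total bilirubin above 2 × ULN. There the instruction is "Repeat ALT, AST, bilirubin, and ALP testing, and perform initial GGT testing, within 48-72 hours with the central laboratory to confirm the results".

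Two provisions allow earlier action. Section 5.6.1 permits withdrawal from study treatment for an adverse event of unacceptable risk, on the judgment of the investigator, Sponsor or medical monitor. Section 5.6.2 adds that "the investigator may discontinue individual participants from the study at any time".

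**The concern.** Because the liver rule applies only after confirmation, the repeat test turns a suspected stopping case into a mandatory one. The window for that repeat is therefore the longest time the written rule lets such a case go unconfirmed.

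The two sections sort participants by different variables. Section 5.6.1 uses enzymes, bilirubin, INR, symptoms and signs. Section 17.1.2 uses enzymes and bilirubin only. The symptom review that opens Section 17.1.2.1 tells the site at once whether a listed symptom is present, but the answer does not change the window.

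Two details suggest an oversight. Section 5.6.1 joins bilirubin and INR as alternatives in one limb, yet Section 17.1.2.2 gives the shorter window to the bilirubin half only. Section 17.1.1 ties the appendix to Sections 8.2.1 and 8.4.3 and does not mention 5.6.1.

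At stake are a few days of dosing in participants with a possible symptomatic liver reaction. Liver safety matters for this drug: SAP Section 1 says the study was terminated after liver enzyme findings in other studies of it.

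**Working it through.** The plan gives no computed figure to reproduce. The check sets the stopping limbs of Section 5.6.1 against the repeat windows of Section 17.1.2, and then converts days to tablets.

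**Cross-classification.** No bilirubin elevation unless stated.

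| Case at first abnormal result | Stop mandatory once confirmed (5.6.1)? | Section that applies | Repeat window |
|---|---|---|---|
| (a) 3 to below 5 × ULN with a listed new symptom or sign | Yes | 17.1.2.1 | up to 1 week |
| (b) 3 to below 5 × ULN with INR above 1.5 | Yes | 17.1.2.1 | up to 1 week |
| (c) 5 to below 8 × ULN, no symptom or sign, INR not above 1.5, for 2 weeks or less | Not yet | 17.1.2.2 | 48–72 hours |
| (d) at least 8 × ULN | Yes | 17.1.2.2 | 48–72 hours |
| (e) 3 to below 5 × ULN with total bilirubin above 2 × ULN | Yes | 17.1.2.2 | 48–72 hours |

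Rows (d) and (e) are aligned. Rows (a) and (b) against (c) are not: the groups that must stop have the longer limit, and the group that need not yet stop has the shorter one. Many jaundiced participants would probably fall in row (e), so row (a) concerns mainly the other symptoms and signs.

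**How far row (b) reaches.** The Section 17.1.2.1 repeat panel does not include INR. The laboratory-test footnote to the Section 15 schedule lists hematology, chemistry and urinalysis, plus serology at Screening, but not coagulation. Section 7.1.1.2.6 lists PT but does not name INR. INR is named as a test in Section 17.1.2.3, which is reached after confirmation under Section 17.1.2.2. Row (b) therefore applies only where an INR happens to be available. Row (a) carries the point.

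**Dosing inputs.** 400 mg twice daily (Section 6.1.4); 400 mg tablets (Section 6.1.2), so 2 tablets a day; 168 days of treatment (Section 7.3.2). Planned course: 168 × 2 = 336 tablets.

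**Tablets at each limit, if dosing continues while the repeat is pending**

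- 17.1.2.1 at 7 days: 7 × 2 = 14 tablets; 14 × 400 = 5,600 mg.
- 17.1.2.2 at 72 hours: 3 × 2 = 6 tablets; 6 × 400 = 2,400 mg.
- 17.1.2.2 at 48 hours: 2 × 2 = 4 tablets; 4 × 400 = 1,600 mg.

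**Differences**

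- Limit against limit: 7 − 3 = 4 days; 14 − 6 = 8 tablets; 8 × 400 = 3,200 mg; 8/336 = 2.4%.
- Against a 48-hour repeat: 7 − 2 = 5 days; 14 − 4 = 10 tablets; 10 × 400 = 4,000 mg; 10/336 = 3.0%.
- If the 17.1.2.1 repeat is also drawn at 72 hours: 3 − 3 = 0 days.
- If it is drawn the next day, against 72 hours: 1 − 3 = −2 days, so the 17.1.2.1 case is confirmed first.

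Laboratory turnaround is not stated and is taken as equal for both tracks.

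**The case against.** The strongest reply is that tiering by enzyme level is a reasonable design. At 5 to below 8 × ULN an early repeat detects a rise to 8 × ULN and supports the rule for elevations lasting more than 2 weeks. That justifies the 48–72 hour window for row (c). It does not explain a looser limit for row (a), where the mandatory stop also depends on the repeat.

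A second reply is that the 1-week figure is a ceiling within text labelled as guidelines, and that the protocol has several routes to earlier action. The unacceptable-risk provision in 5.6.1 needs no repeat test. The investigator may discontinue a participant at any time. Section 8.4.1 recognises holding treatment as an action. Serious events must be reported immediately, with the form due within 24 hours (Section 8.4.2.1). Safety laboratory data are reviewed throughout (Section 8.6). All of this stands and keeps the point small. But the same discretion exists at 5 to below 8 × ULN, and there the protocol still fixed a shorter limit.

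A third reply is that the special-interest event definitions are blacked out in Protocol Section 8.4.3 and SAP Section 4.4.3, and Section 17.1.1 refers to 8.4.3. Related wording may sit there, so the claim is confined to the visible text.

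A reader might infer more than this: that the protocol keeps symptomatic participants on drug for a week, or that the mild grade in Section 8.2.1 or the later follow-up schedule is wrong. The documents do not support those readings. Confirmation triggers the mandatory stop and does not bar an earlier one. The grading serves adverse-event recording. Closer later follow-up of participants at 5 to below 8 × ULN, who may remain on drug, is coherent.

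**Conclusion.** On the visible text, the limit for the first confirmatory repeat is longer for a group that must stop once confirmed than for a group that need not yet stop. The mismatch covers only 3 to below 5 × ULN without bilirubin elevation, and only the time to the first repeat.

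The figures of 4 days limit against limit, or 5 days against a 48-hour repeat, assume that dosing continues, that the full week is used and that laboratory turnaround is equal. In practice the difference may be zero or negative. The number of affected participants cannot be estimated from the documents and is probably small.

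Three participants were randomized and on study drug when termination was announced (SAP Section 1), so the remaining value lies in any reuse of this liver text. That reuse is an assumption; no document mentions it. Severity is minor, and the change is a cheap improvement.

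**What to change.** Add one sentence to Section 17.1.2.1, for example: *If the initial ALT or AST is at least 3 × ULN and any symptom or sign listed in Section 5.6.1 is present, or INR is known to be above 1.5, perform the confirmatory repeat within 48–72 hours (sooner if clinically indicated), pending confirmation under Section 5.6.1.*

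Two other wordings are less suitable. Restricting 17.1.2.1 to participants who meet no 5.6.1 criterion would exclude nobody at this stage, because confirmation is part of the criterion. Moving these cases wholly into 17.1.2.2 would also bring weekly testing, the extended serology and an ultrasound after confirmation, which this point does not call for.

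Leave the 8.2.1 grading and the post-confirmation work-up unchanged. Holding study drug while the repeat is pending is optional. The cost is a few earlier blood draws or unscheduled visits.
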